9.3.3 EQ-5D Patient Questionnaire

EQ-5D is a standardized measure of health status developed by the EuroQol Group in order to provide a simple, generic measure of health for clinical and economic appraisal. The EQ-5D as a measure of health-related quality of life, defines health in terms of 5 dimensions: mobility, self-care, usual activities, pain/discomfort, and anxiety/depression. Each dimension can take one of three responses (3 ordinal levels of severity): “no problem” (1); “some problems” (2); “severe problems” (3). Overall health state is defined as a 5-digit number. Health states defined by the 5-dimensional classification can be converted into corresponding index scores that quantify health status, where 0 represents “death” and 1 represents “perfect health” (see [Section 17](#), Appendix J) ([36](#)). If response to one or more dimension is missing, the index score will be missing.

EQ-5D variables include response of each EQ-5D items, index score, and absolute change of index score from the randomization visit (Week 0) ([36](#)).

9.4 APPROPRIATENESS OF MEASUREMENTS

The efficacy and safety endpoints used in this study are standard for the evaluation of post-ACS patients with hypercholesterolemia (refer to [Section 4](#) for details).

10 STUDY PROCEDURES

For all study site visits except the randomization visit (Visit 1/Week 0), a time frame of 7 days before and after the scheduled study site visit will be allowed. For all study site visits after the randomization visit (Visit 1/Week 0), if a visit date is not kept, the next visit is scheduled according to the original schedule as outlined in [Section 1.2](#).

Evaluation IVUS imaging:

The evaluation IVUS imaging will be performed in the same vessels of the initial IVUS imaging at the ACS diagnosis. The Investigator can schedule the evaluation IVUS imaging within 2 weeks before and after the EOT (Week 36; between Week 34 and Week 38). The detailed procedures of IVUS imaging are described in the specific manual. If the evaluation IVUS study cannot be performed by the EOT visit (Week 36) in patients of the alirocumab arm, Praluent® will be administered at Week 36 after data collection listed in the EOT visit (see [Section 10.1.1.1.5](#)), and the evaluation IVUS imaging can be performed before Week 38, while the effect of alirocumab remains. For patients in the SoC arm, the evaluation IVUS imaging should be performed between Week 34 and Week 36 as in the alirocumab arm. If patients cannot undergo the evaluation IVUS imaging by Week 36, all efforts should be made to perform the evaluation IVUS imaging by Week 38.

Blood sampling:

The blood sampling has to be performed in the morning under fasting conditions, which is defined as an overnight fast no less than 8 hours that consist of no food or liquid intake other than water with exception of to do so otherwise by Investigator/sub-Investigator's medical judgment, throughout the study.

The blood sample will be used to measure lipid parameters [TC, LDL-C, HDL-C, TG, non-HDL-C, Apo B, Apo A-1, Apo B/Apo A-1 ratio, Lp(a)], hematology (red blood cell count, hemoglobin, hematocrit, white blood cell count and differential count, platelet count), blood chemistry, HbA1c, hs-CRP, hepatitis B virus antibody, hepatitis C virus antibody, etc (see also [Section 1.2](#)).

Alcohol consumption within 48 hours and intense physical activities within 24 hours preceding the blood sampling are discouraged.

Note: If a patient is not in fasting conditions, the blood sampling will be postponed and a new appointment will be given the day after (or as close as possible to this date) to the patients with instruction to fast.

Laboratory tests:

The laboratory data are collected in accordance with the study schedule described in [Section 1.2](#). It is noted that the lipid panels 1, 2, hepatitis C virus antibody, hepatitis B total core antibody (HBc-ab), hs-CRP, and HbA1c will be measured by the central laboratory (and at each study site if necessary).

- Hematology
- Chemistry including liver function enzymes, LDH, and CPK
- Lipid panel 1: TC, calculated and directly measured LDL-C, HDL-C, TG, and non-HDL-C
- Lipid panel 2: Apo B, Apo A-1, Apo B/Apo A-1, and Lp(a)
- Hepatitis C virus antibody: positive test will be confirmed with reflexive testing at each study site
- Hepatitis B virus surface antigen, surface antibody, and total core antibody: positive test that suggests active infection (positive surface antigen and antibody) or viral carrier (positive total core antibody) will be confirmed with reflexive testing at each study site.

Note: The results of hepatitis B virus surface antigen and antibody results will be collected from each study site. Hepatitis B virus total core antibody will be measured by the central laboratory at the randomization visit (Week 0). Hepatitis B virus DNA will be measured immediately if positive hepatitis B virus total core antibody results.

- HbA1c
- hs-CRP
- Urine pregnancy test
- Serum pregnancy test

Decision trees for the management of certain laboratory abnormalities by Sponsor are provided in [Section 17](#), Appendix F, and Appendix G, and should be followed by Investigators/sub-Investigators.

Other endpoint assessment methods:

All other blood parameters will also be measured at each study site during the study (as per the schedule in [Section 1.2](#), on blood samples taken preferably in the morning in fasting conditions described above [see [Section 10.1.1](#)]). Alcohol consumption within 48 hours and intense physical activities within 24 hours preceding the blood sampling are discouraged.

Physical examination:

A physical examination should be performed at the time points indicated in the study schedule flowchart of [Section 1.2](#). If a new clinically significant abnormality or worsening from baseline is detected after randomization, as should be reported as AE and further clinical investigations and/or specialist consultation should be considered as per the Investigator/sub-Investigator's medical judgment.

Blood pressure / heart rate:

It is recommended that blood pressure is measured in the sitting position under the same conditions each time, approximately at the same time of the day, on the same arm, with the same

apparatus (after the patient has rested in sitting position for at least 5 minutes). Both systolic and diastolic blood pressure should be recorded. It should be noted that blood pressure should be measured in both arms at the randomization visit (Week 0). The arm with the highest diastolic blood pressure will be used to measure the blood pressure throughout the study. The highest blood pressure value will be recorded in the e-CRF.

The heart rate will also be measured at the time of blood pressure measurement.

Note: In cases with hypertension (high blood pressure values) (within 4 weeks prior to the randomization or after ACS onset and prior to the randomization) the Investigator/sub-Investigators is responsible for the optimization of the patient's treatment to achieve blood pressure target as defined by local guidelines (Japanese Society of Hypertension) or the Seventh Report of the Joint National Committee on Prevention, Detection, Evaluation, and Treatment of High Blood Pressure (JNC7).

Body weight and height:

Body weight should be obtained with the patient wearing undergarments or very light clothing and no shoes, and with an empty bladder. The same scale should be used throughout the study. The use of calibrated balance scales is mandatory. Self-reported weights are not accepted. Patients must not read the scale themselves. Height should be measured and self-reported heights are not accepted.

EQ-5D patient questionnaire:

Collection of EQ-5D patient questionnaire will be carried out in all patients at each scheduled visit (5 visits) by Investigator, or a person designated by the Investigator.

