- n* Hepatitis B virus DNA will be measured promptly if hepatitis B virus total core antibody comes back positive.

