- If patients have not been on any statin therapy at ACS onset, either atorvastatin 10 mg/day or rosuvastatin 5 mg/day is started immediately after the ACS diagnosis, and LDL-C is not adequately controlled with statin at 2 to 4 weeks after the ACS diagnosis (in principle, LDL-C target level ≥ 100 mg/dL, but this may not apply if the responsible physician considers the LDL-C level inadequate on statin. Patients who have LDL-C < 70 mg/dL cannot be enrolled).

I 03. Patients who has stenosis of at least $>50\%$ on coronary angiography within 1 week after the ACS onset, and has analyzable coronary IVUS image. The evaluated segment of IVUS is a segment where a physician considers the IVUS imaging is possible (regardless of culprit vessels or not culprit vessels) other than the culprit lesions.

I 04. Patients aged ≥ 20 years old at ACS diagnosis.

I 05. Patients who meet any of the following conditions.

- Negative hepatitis B virus surface antigen, negative total hepatitis B virus core antibody, and negative hepatitis C virus antibody.
- Negative hepatitis B virus surface antigen, positive total hepatitis B virus core antibody, negative hepatitis B virus DNA and negative hepatitis C virus antibody.

I 06. Written informed consent.

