- Serum and urine pregnancy tests (women of childbearing potential [WOCBP]).
- Confirm and record compliance with background LMT regimen including NIMPs.
- Fasting blood sample listed below will be collected and measured.
- Hematology and chemistry.
 - TC, calculated and directly measured LDL-C, HDL-C, TG, non-HDL-C (central laboratory).
 - Apo B, Apo A-1, Apo B/Apo A-1, Lp(a) (central laboratory).
 - HbA1c (central laboratory).
 - hs-CRP (central laboratory).
 - Hepatitis B virus antibody (Hepatitis B virus total core antibody is tested at the central laboratory).
 - Hepatitis C virus antibody titer (central laboratory).

Note: Additional blood samples can be obtained for measurement of above listed items and others at the study site by Investigator's judgment as needed.

- If the patient's eligibility (and fasting status) is confirmed, contact the registration center for randomization. The Investigator/sub-Investigator must not administer IMP without notifying the registration center.
- When the Investigator confirms the patient is randomized to the alirocumab arm and has completed fasting blood sample collection and assessments of all evaluations planned at this randomization visit (Visit 1), the first Praluent® injection will be performed at the study site following the patient injection instruction.
- The patient should be observed for at least 30 minutes after Praluent® administration.
- If patient is randomized to the SoC arm, ongoing LMTs will be continued unless modification of LMTs is made by the Investigator's medical judgment.
- For the patient who is randomized to the alirocumab arm, an appointment will be given for next Praluent® administration visit (Week 2 / D15).
- For the patient who is randomized to the SoC arm, an appointment will be given for next on-site visit (Visit 2 / Week 4 / D29). The patient should be instructed to visit the study site in the morning under fasting conditions, which is defined as an overnight fasting no less than 8 hours that consist of no food or liquid intake, other than water unless exception made by Investigator's medical judgment.
- Transfer IVUS imaging data to the central reading laboratory.

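### Inclusion criterion I 05 needs hepatitis B core and hepatitis C antibody results that the schedule obtains only from the Week 0 sample, at the visit where patients are randomized and first injected

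*Protocol*

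**What the plan says.** Protocol Section 7.1, criterion I 05, offers two routes to eligibility.

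- Route one: "Negative hepatitis B virus surface antigen, negative total hepatitis B virus core antibody, and negative hepatitis C virus antibody".
- Route two: "Negative hepatitis B virus surface antigen, positive total hepatitis B virus core antibody, negative hepatitis B virus DNA and negative hepatitis C virus antibody".

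The flow chart in Section 1.2 places both antibody tests in the Week 0 / Day 1 column, together with randomization and the first Praluent administration. Section 10 (Laboratory tests) says of the core antibody: "Hepatitis B virus total core antibody will be measured by the central laboratory at the randomization visit (Week 0". The blood-sample list in Section 10.1.1.1 for the randomization visit repeats this for both antibodies: "Hepatitis B virus antibody (Hepatitis B virus total core antibody is tested at the central laboratory" and "Hepatitis C virus antibody titer (central laboratory".

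Hepatitis B DNA has no column in the flow chart. Footnote n says only: "Hepatitis B virus DNA will be measured promptly if hepatitis B virus total core antibody comes back positive".

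For a patient allocated to alirocumab, Section 10.1.1.1 says that once the investigator confirms the allocation and that the patient "has completed fasting blood sample collection and assessments of all evaluations planned at this randomization visit (Visit 1), the first Praluent® injection will be performed".

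**The concern.** An inclusion criterion can screen patients only if its result is known before allocation. As scheduled, two of the three serology results that I 05 needs come from blood drawn on the day of randomization and sent to a central laboratory. The fourth, conditional result (DNA) is triggered by one of those two. A site that follows the visit flow literally has nothing in hand on these items when it contacts the registration center.

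The stakes are exposure of a patient who should have been screened out, and an eligibility deviation that the protocol's own schedule would have produced.

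**Working it through.** No arithmetic applies and the plan states no figure to reproduce. The check sets the timing of each eligibility result beside the point of randomization.

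| Result used for eligibility | When the protocol obtains it | Tied to a time before randomization? |
|---|---|---|
| Hepatitis B surface antigen | Results from ACS diagnosis/PCI; if not done, measured before the randomization visit (Section 10.1.1.1) | Yes |
| Lipids for selection | Measured at the site for patient selection (Section 1.2, footnote h) | Yes |
| Serum pregnancy test | Negative site result needed before the randomization visit (Section 7.2.3, note to E 12) | Yes |
| Hepatitis B core antibody | Central laboratory, Week 0 sample (Sections 1.2, 10, 10.1.1.1) | No |
| Hepatitis C antibody | Central laboratory, Week 0 sample (Sections 1.2, 10, 10.1.1.1) | No |
| Hepatitis B DNA, if core antibody positive | After the core antibody result returns (Section 1.2, footnote n; Section 10) | No |

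1. **Could Visit 1 be spread over several days?** The flow chart assigns it Day 1 with no window, and Section 10 excludes it from the seven-day allowance given to other visits. Nothing says that the visit may pause while central results are awaited.
2. **Does the injection wait for results?** Its stated condition is that blood has been collected and the planned assessments done. Receipt of the central serology is not mentioned.
3. **Does another rule require eligibility first?** Yes, in four places. Footnote a of Section 1.2 puts eligibility assessment before Visit 1. Section 10.1 limits enrollment to patients who meet the criteria. Section 10.1.1.1 has the registration center make a final check before it communicates the arm, and has the site confirm eligibility before it contacts the center for randomization.
4. **Can both sets of rules be followed?** Only if the results exist before Visit 1 or return the same day. No section schedules an earlier core antibody, hepatitis C antibody or DNA result, gives a central turnaround time, or tells the site to wait.
5. **What happens to a patient found to fail later?** Section 10.3.3 has only general clauses and no specific criterion for this case. Section 10.3 asks that patients stay in the study as long as possible. Section 10.3.1, however, makes restart after a temporary interruption depend on the selection criteria still being met, which such a patient would not satisfy.
6. **What happens in the analysis?** The modified intent-to-treat definition (SAP Section 2.3.1.1) does not depend on I 05, and I 05 is not among the inclusion criteria listed for per-protocol exclusion (SAP Section 2.3.1.2).

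**The case against.** The strongest reply is that the protocol forbids the outcome. The four checks in step 3 mean that a site without an I 05 result cannot confirm eligibility, so randomizing that patient would be a breach. There is also a local route. Section 10 lets sites run these antibodies when needed, and a note in Section 10.1.1.1 lets the investigator draw extra samples for the listed tests. A central Week 0 sample is compatible with earlier local screening, as the lipid arrangements show.

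Much of this stands. A reader might infer that the protocol permits randomization of ineligible patients; it does not. But the checks demand a result that the written schedule does not supply in time. Local testing is discretionary, is not linked to I 05 and has no timing before randomization. Footnote i of Section 1.2 also leaves these two antibodies out of the safety laboratory data collected from sites. What is explicit for surface antigen, lipids and pregnancy is left to inference here.

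Three stronger readings are tempting and are not supported.

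- **Patients found to fail I 05 are withdrawn after randomization.** No section states such a rule.
- **The primary result is biased.** Serostatus precedes randomization, so it is balanced between arms in expectation, and the primary population keeps these patients in their randomized arm.
- **The hepatitis C seroconversion analysis loses its baseline.** SAP Section 2.4.5.3 restricts that analysis to patients with a negative baseline, and its Table 2 labels an antibody-positive patient with no detectable RNA as negative. A Week 0 sample taken before dosing can supply the baseline. A patient who fails I 05 only on hepatitis B has no hepatitis C baseline problem.

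**Conclusion.** The point holds as a contradiction between the testing schedule and the eligibility checks. I 05 depends on results with no scheduled time before randomization, while other sections require eligibility to be settled first. The risk is that a patient who fails I 05 is randomized, and in the alirocumab arm injected, before the result is known. This is a matter of safety and protocol compliance; no effect on the primary estimate is shown.

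The size cannot be computed. The documents give no seroprevalence, no central turnaround time and no indication of how many sites would test locally. A positive core antibody alone does not fail I 05: with surface antigen and hepatitis C antibody negative, DNA must also be positive. With 1:1 allocation, about half of any such patients would be in the arm injected at Visit 1.

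The conclusion assumes that central results do not routinely return within the visit. If both antibodies did come back the same day, the gap would narrow to the DNA result, which starts only after a positive core antibody.

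**What to change.** Reconcile the flow chart (Section 1.2), the Laboratory tests text in Section 10 and the Visit 1 list in Section 10.1.1.1 with I 05. State that the hepatitis B core antibody, the hepatitis C antibody and any required hepatitis B DNA result, from either the site or the central laboratory, must be available before the registration center is contacted. Existing results may be used; otherwise a sample is drawn after consent and before Visit 1. The Week 0 central sample can remain as the baseline measurement. The protocol should also say how a result that turns positive after randomization is recorded and handled; the content of that rule is for the clinical team.

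The cost is mainly wording, with at most one sample moved earlier. Consent may be taken at any time from ACS diagnosis to Visit 1, and Section 10.1 requires at least two weeks of stable statin before randomization. Patients who start or switch statin at diagnosis therefore have time for the test. Patients already on a qualifying statin may have a shorter interval. The one real downside is that results, including any DNA result, must arrive within four weeks of the ACS diagnosis.

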10.1 VISIT SCHEDULE

Patients with hypercholesterolemia, who develop ACS and undergo successful therapeutic intervention such as PCI (stent placement), and IVUS imaging, are the target subjects of the current study. All patients have to have been received stable statin therapy with either atorvastatin ≥ 10 mg/day or rosuvastatin ≥ 5 mg/day for at least 2 weeks prior to the randomization visit (Visit 1).

Between the onset of ACS and the randomization visit (within 4 weeks prior to the randomization visit), the patient will receive verbal information concerning the aims and methods of the study, its constraints and risks, and the study duration, and will be provided of a written summary. The written informed consent must be signed by the patient and the Investigator prior to any study activity. Only patients who meet the inclusion/exclusion criteria as noted in [Section 7](#) will be enrolled to the study. Women of childbearing potential will be instructed to use a medically approved contraceptive method throughout the entire study period.

10.1.1 Open-label treatment period

For each on-site visit, the patient should visit the study site in the morning under fasting conditions, which is defined as an overnight fasting no less than 8 hours that consist of no food or liquid intake other than water with the exception made by Investigator's medical judgment.

During the open-label treatment period, the patient will have 5 on-site visits, and 14 Praluent® administration visits[§] for patients in the alirocumab arm or 5 phone-call interviews for patient in the SoC arm. Data on IMP/NIMP compliance and any AE/SAE including CV events will be recorded in both study arms after the randomization visit (Week 0) to the EOT visit (Week 36).

- 5 on-site visits: Weeks 0, 4, 12, 24, and 36.
- 14 Praluent® administration visits (alirocumab arm only)[§]: Weeks 2, 6, 8, 10, 14, 16, 18, 20, 22, 26, 28, 30, 32, and 34.

[§]: If the evaluation IVUS imaging cannot be performed by Week 36, patients will receive an additional Praluent® dose at Week 36. The evaluation IVUS imaging must be performed within 2 weeks of Week 36 on-site visit.

- If patients perform self-injection of Praluent® at home, they must visit the study site at least every 4 weeks, and at Weeks 0, 4, 12, 14, 24, and 36 regardless of the timing of the first self-injection.
- 5 phone-call interviews (SoC arm only); Weeks 8, 16, 20, 28, and 32.

10.1.1.1 Study site visit

10.1.1.1 Randomization visit (Visit 1 / Week 0 / D1)

Blood sampling should be completed before IMP administration.

This visit includes:

- On-site visit.
- Complete and collect written informed consent for the study by the randomization visit. Patient number will be allocated by the registration center. The patient number is composed of a 9-digit number containing the 3-digit country code, the 3-digit center code, and the 3-digit patient chronological number (3-digit patient chronological number is 001 for the first patient screened in a center, 002 for the second patient screened in the same center).

Note: The written informed consent can be obtained any time between ACS diagnosis and the randomization visit (see [Section 1.2](#)).

- Confirm inclusion and exclusion criteria.
- Collect information about therapeutic intervention such as ACS culprit vessels, IVUS imaging locations (refer to [Section 17](#), Appendix D for vessel locations), and types of stent placed at the PCI (BMS or DES).

- Contact the registration center to notify the patient enrollment. After the final confirmation of inclusion and exclusion criteria at the registration center, the arm to which the patient randomized to is communicated.
- Demographics (age, gender, race, ethnicity).
- Collect contact information (address, email, home and cell phone numbers) of the patient, patient's family members, and patient's primary care physician / cardiologist.
- Patient's medical and surgical history (including menopausal status, and family history), alcohol habits, smoking habits, lipid parameters including LDL-C used for the study eligibility, and HbA1c.
- Collect patient's history of CV disease.
- Record use of LMT including statins and prescription or over-the-counter non-statin LMTs within 1 month prior to Visit 1.
- Record of all concomitant medications including CV medications.
- Collection of adverse events including CV events (if any).
- Collection of results of hepatitis B virus surface antigen and antibody tested at the time of ACS diagnosis and PCI.

Note: If the hepatitis B virus surface antigen and antibody titers are not checked, they must be measured prior to the randomization visit and the results must be recorded at the randomization visit (see [Section 7.1](#)).

- Physical examination including vital signs: heart rate and sitting SBP and DBP.
- Body weight and height.
- EQ-5D patient questionnaire.
- Serum and urine pregnancy tests (women of childbearing potential [WOCBP]).
- Confirm and record compliance with background LMT regimen including NIMPs.
- Fasting blood sample listed below will be collected and measured.
- Hematology and chemistry.
 - TC, calculated and directly measured LDL-C, HDL-C, TG, non-HDL-C (central laboratory).
 - Apo B, Apo A-1, Apo B/Apo A-1, Lp(a) (central laboratory).
 - HbA1c (central laboratory).
 - hs-CRP (central laboratory).
 - Hepatitis B virus antibody (Hepatitis B virus total core antibody is tested at the central laboratory).
 - Hepatitis C virus antibody titer (central laboratory).

Note: Additional blood samples can be obtained for measurement of above listed items and others at the study site by Investigator's judgment as needed.

- If the patient's eligibility (and fasting status) is confirmed, contact the registration center for randomization. The Investigator/sub-Investigator must not administer IMP without notifying the registration center.
- When the Investigator confirms the patient is randomized to the alirocumab arm and has completed fasting blood sample collection and assessments of all evaluations planned at this randomization visit (Visit 1), the first Praluent® injection will be performed at the study site following the patient injection instruction.
- The patient should be observed for at least 30 minutes after Praluent® administration.
- If patient is randomized to the SoC arm, ongoing LMTs will be continued unless modification of LMTs is made by the Investigator's medical judgment.
- For the patient who is randomized to the alirocumab arm, an appointment will be given for next Praluent® administration visit (Week 2 / D15).
- For the patient who is randomized to the SoC arm, an appointment will be given for next on-site visit (Visit 2 / Week 4 / D29). The patient should be instructed to visit the study site in the morning under fasting conditions, which is defined as an overnight fasting no less than 8 hours that consist of no food or liquid intake, other than water unless exception made by Investigator's medical judgment.
- Transfer IVUS imaging data to the central reading laboratory.

